2.4.2 Statistical hypothesis, model, and method of analysis

Confirmed ORR will be calculated as the proportion of subjects that have a confirmed response relative to the total number of subjects in the corresponding analysis population.

Confirmed ORR will be analyzed using an integrated analysis across the histologic cohorts with the hierarchical model. Model-based interim decision rules have been used through the study to identify whether one or more histologic cohorts halt enrolment early for futility/harm or benefit based on efficacy data.

Model-based decision rules for the final analysis are provided in the protocol. At the final analysis, a minimum of 2 subjects will be required in a histologic cohort in order to meet statistical success. A histologic cohort will be declared active if the posterior probability that the ORR exceeds its corresponding historical control is sufficiently high (>92%) based on the hierarchical model. That is,

$$P(\pi_j > C_j \% \mid \text{current data}) > 92\%, \text{ for the } j\text{-th histology.}$$

This decision rule has been determined based on extensive simulations of the study design as described in the protocol.

A summary of the Bayesian hierarchical model-based analysis will be provided. For each histology the following measures will be reported: the total number of subjects, the protocol-specified historical control response rate, the estimated response rate and 95% credible interval (based on the posterior mean and 2.5% and 97.5% percentiles), and the posterior probability that the ORR exceeds its corresponding historical control response rate.

Descriptive summaries of best confirmed response along with the corresponding 95% exact confidence intervals will be provided for each response criteria for the varying histologic cohorts in order to characterize the observed response data and support the model-based analyses for ORR. Best response and ORR will be presented for the primary cohort, expansion cohort and primary and expansion combined for each histology for which an expansion cohort was opened.

The model-based analysis of ORR and supporting summaries of best confirmed response will be re-produced based on the BRAF V600E Population.

All supporting individual response and lesion data will be listed. For histologic cohorts using RECIST 1.1 (ATC, BTC, GIST, ASI), a listing of all investigator-assessed lesion assessments will be provided. For glioma cohorts (WHO Grade 1 or 2 and WHO Grade 3 or 4), listings of measureable, non-measureable, and new lesions will be provided. For HCL, separate listings of lymph nodes including palpable lymph nodes will be provided. For MM, supportive laboratory results including serum and urine monoclonal protein, serum free light chain (FLC) and FLC ratio will be listed.

2.4.3 Handling of missing values/censoring/discontinuations

Response assessments occurring after disease progression or the start of new anti-cancer therapy will not be included in the determination of best response. Response assessments occurring after end of study treatment but before disease progression or the start of new anti-cancer therapy will be included. There will be no imputation of missing values.

2.4.4 Supportive analyses

Descriptive summaries of best response based on independent radiology review will be provided for the ATC, BTC, ASI, WHO Grade 1 or 2 Glioma and WHO Grade 3 or 4 Glioma cohorts as sensitivity analyses. Specifically, the best response based on independent reviewer assessment will be determined programmatically and summarized in the same way as the best response based on investigator assessment.

An assessment of the concordance between the investigator-assessed response and independent reviewer-assessed response will be performed for each of the cohorts listed above. Kappa coefficient will be reported along with the corresponding 95% confidence interval.

The concordance rate is calculated as percent agreement (the proportion of best response that agree between investigator assessment and independent reviewer assessment):

$$\text{Percent agreement} = \frac{\# \text{ of matched responders} + \# \text{ of matched non - responders}}{\text{total \# of subjects assessed}}$$

If ORR from either investigator assessment or independent reviewer assessment for a subject is missing, then the subject will be excluded from the calculation of the concordance rate.

An overall listing of subject response data based on independent radiology review will be provided alongside the investigator assessed responses for the ITT population in the ATC, BTC, ASI, GIST, WHO Grade 1 or 2 Glioma and WHO Grade 3 or 4 Glioma cohorts. This listing will display both independent reviewer-assessed and investigator assessed response evaluations, the best confirmed responses, and BRAF V600E central confirmation status.

2.5 Analysis of the key secondary objective

There is no key secondary objective for this study.

2.6 Analysis of secondary efficacy objective(s)

The secondary efficacy endpoints include duration of response (DoR), progression free survival (PFS) and overall survival (OS). The secondary efficacy endpoints will be analyzed for ATC, BTC, ASI, WHO Grade 1 or 2 Glioma, WHO Grade 3 or 4 Glioma, MM and HCL cohorts. The analyses of the secondary endpoints will take place once all patients have either died or been transitioned off the study. The main population for efficacy analyses is ITT. The BRAF V600E population will be used for supportive analyses of efficacy.

2.6.1 Duration of response

For the subset of subjects who show a confirmed response as defined for each cohort in [Error! Reference source not found. 2.4.1](#), duration of response (DoR) is defined as the time (in weeks) from the first documented evidence of response (the first response prior to confirmation) until the time of documented disease progression or death due to any cause.

For the cohorts assessed using RECIST 1.1 and RANO criteria, the analysis of DoR will be based on radiological response from investigator assessment. The date of disease progression is defined as the date of radiological disease progression based on the appropriate disease response criteria. Clinical progression, defined as investigator assessed clinical progression in the absence of radiological confirmation, is not considered a progression event in this analysis. Specifically, in the event of clinical progression leading to discontinuation of study treatment and radiological assessment, if radiological assessments do not indicate radiological progression, then the subject will be censored at the time of last radiological assessment. If a subject has not progressed, not died, and not started new anti-cancer therapy, DoR will be censored at the date of the last adequate assessment.

For the HCL cohort, the overall investigator-assessed response will be used to determine timing of response and/or progression. Relapsed disease will be considered as progression for the analysis.

Details of censoring after extended time without adequate assessment are given in section 4.2.

For subjects who receive subsequent anti-cancer therapy, the following rule will apply:

- If anti-cancer therapy is started without documented progression or is started prior to progression, then DoR will be censored at the date of the last adequate disease assessment that is no later than the date of initiation of anti-cancer therapy (i.e. if disease assessment occurs on the same day as the start of new anti-cancer therapy then the assessment will be used, as it will be assumed that the assessment occurs prior to the administration of new anti-cancer therapy).

DoR based on the investigator response will be summarized for ATC, BTC, ASI, WHO Grade 1 or 2 Glioma, WHO Grade 3 or 4 Glioma and HCL cohorts. If data warrant, Kaplan-Meier method will be used to summarize DoR descriptively and graphically. The median DoR and the first and third quartiles will be presented, along with corresponding 95% confidence intervals. Brookmeyer-Crowley method will be used for the confidence interval calculation. DoR will also be summarized at 6 months, 12 months and 24 months.

Listing of DoR based on investigator assessment will also be provided.

In addition, swim lane plots will be generated for response data based on investigator assessment. These plots will present the best confirmed response category, duration of treatment, time of the first response, duration of response, time of the first disease progression based on radiological assessment and study treatment status at the time of data cut-off for the analysis.

As a sensitivity analysis, DoR based on independent radiology review will be summarized and listed for the ATC, BTC, WHO Grade 1 or 2 Glioma, and WHO Grade 3 or 4 Glioma cohorts, including the estimated median, first and third quartiles, 6 and 12 month Kaplan-Meier estimates. The derivation of DoR based on independent radiology review is similar to that based on the investigator assessment.

For the HCL cohort only, and for the subset of subjects who have a confirmed complete response (with or without MRD), the complete response duration will be calculated as the time from first CR until the earliest of the first subsequent non-CR adequate assessment or death due to any cause. Censoring rules will be applied the same as with Duration of Response. Kaplan-Meier estimates will be used to estimate the median and quartiles of the complete response duration as well as the complete response duration at 180 days. The number and proportion of

the ITT population with complete response duration of at least 180 days will be calculated along with the corresponding Clopper-Pearson exact confidence interval. The time to first confirmed complete response and time to first confirmed overall response will both be summarized with the minimum, maximum, 1st and 3rd quartiles and median displayed in weeks. Only confirmed responders will be included in each of the summaries.

Summaries of reasons for censoring DoR by both investigator assessment and independent radiology review will be produced with additional information about censoring due to COVID-19 related protocol deviations. The number and percentage of subjects with each censoring reason (1. PD or death after ≥ 2 consecutive missed visits, 2. New anti-cancer treatment started prior to documented PD, 3. No baseline (or adequate post-baseline) assessments, 4. No progression or death, separated into follow-up ended and follow-up ongoing) will be displayed along with relevant COVID-19 related censoring reasons (study withdrawal due to COVID-19 and missing visits due to COVID-19) derived from protocol deviations data. Further details of these outputs are given in the programming notes to the TFL shells.

2.6.2 Progression-free survival

Progression-free survival (PFS) is defined as the interval (in weeks) between the first dose of study treatment and earlier date of disease progression or death due to any cause.

For the cohorts assessed using RECIST 1.1 and RANO criteria, the primary analysis of PFS will be based on radiological response from investigator assessment. The date of disease progression is defined as the date of radiological progression based on imaging data. Subjects who do not meet the RECIST 1.1 or RANO criteria for progression and are still alive will be censored. Clinical progression, defined as investigator assessed clinical progression in the absence of radiological confirmation, is not considered a progression event in this analysis. Specifically, in the event of clinical progression leading to discontinuation of study treatment and radiological assessment, if radiological assessments do not indicate radiological progression, then the subject will be censored at the time of last radiological assessment. If a subject has not progressed, not died, and not started new anti-cancer therapy, PFS will be censored at the date of the last adequate assessment. For the HCL cohort, the overall investigator-assessed response will be used to determine timing of progression.

Details of censoring after extended time without adequate assessment are given in section 4.2.

For subjects who receive subsequent anti-cancer therapy, the following rule will apply:

- If anti-cancer therapy is started without documented progression or is started prior to progression, then PFS will be censored at the date of the last adequate disease assessment that is no later than the date of initiation of anti-cancer therapy (i.e. if disease assessment occurs on the same day as the start of new anti-cancer therapy then the assessment will be used, as it will be assumed that the assessment occurs prior to the administration of new anti-cancer therapy).
- If a subject does not have an adequate post-baseline assessment that is no later than the date of initiation of anti-cancer therapy, PFS will be censored at the date of the first dose. If any adequate post-baseline assessment exists after the date of initiation of anti-cancer therapy, the reason for censoring will be recorded as “new anti-cancer treatment started prior to disease progression”. Otherwise if no adequate post-baseline assessments exist,

the reason for censoring will be recorded as “no baseline (or post-baseline adequate) tumor assessments”.

PFS based on the investigator assessment will be summarized descriptively and graphically using Kaplan-Meier methods. The Kaplan-Meier estimate for the median progression-free survival time and the first and third quartiles will be determined along with approximate 95% confidence intervals. Brookmeyer-Crowley method will be used for the confidence interval calculation. Kaplan-Meier estimate of PFS at 6 months, 12 months and 24 months will be summarized.

Listing of progression free survival based on investigator assessment will also be provided.

As a sensitivity analysis, PFS based on independent reviewer assessment will be summarized and listed (except for the MM and HCL cohorts which have no independent review) similarly as that of PFS based on investigator assessment.

Summaries of reasons for censoring PFS by both investigator assessment and independent radiology review will be produced with additional information about censoring due to COVID-19 related protocol deviations. The number and percentage of subjects with each censoring reason (1. PD or death after ≥ 2 consecutive missed visits, 2. New anti-cancer treatment started prior to documented PD, 3. No baseline (or adequate post-baseline) assessments, 4. No progression or death, separated into follow-up ended and follow-up ongoing) will be displayed along with relevant COVID-19 related censoring reasons (study withdrawal due to COVID-19 and missing visits due to COVID-19) derived from protocol deviations data. Further details of these outputs are given in the programming notes to the TFL shells.

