Further details on response confirmation criteria for each histological cohort will be provided in the RAP. Subjects with unknown or missing response will be treated as non-responders; that is, they will be included in the denominator when calculating the percentage.

The observed confirmed ORR will be reported at the final analysis for each histology. The estimates along with 95% exact confidence interval (CI) will be provided.

Bayesian inference based on summary statistics from the posterior distributions of each ORR will be reported. The posterior mean and posterior 2.5% and 97.5% percentiles of the ORR will be calculated for each histology. In addition, the posterior probability that the ORR exceeds its corresponding historical control will be reported for each histology.

Duration of response for the subset of subjects who have a confirmed response (See [Table 31](#)) is defined as the time from first documented evidence of response until the first documented sign of disease progression or death. Duration of response will be summarized descriptively for each histology, if data warrant, using Kaplan-Meier medians and quartiles. Details on rules for censoring will be provided in the RAP.

Progression-free survival (PFS) is defined as the time from the date of enrollment to the earliest date of progression or death. Progression-free survival (PFS) will be summarized by histology, if data warrant, using Kaplan-Meier quartile estimates along with 2-sided 95% CIs. If the subject does not have a documented date of progression or death, PFS will be censored at the date of the last adequate assessment. Further details on rules for censoring will be provided in the RAP. Progression-free survival (PFS) will be reported at the time of final primary analysis for overall response rate (ORR), regardless of the maturity of the data, and then updated at the final analysis.

Overall Survival (OS) is defined as the time from the date of enrollment to the date of death due to any cause. Censoring will be performed using the date of last known contact for those who are alive at the time of analysis. Overall survival (OS) will be summarized by histology, if data warrant, at the time of final primary analysis for overall response rate (ORR), regardless of the maturity of the survival data, and then updated at the final analysis.

Further details including possible sensitivity analyses will be provided in the RAP.

[REDACTED]

[REDACTED]

[REDACTED]

[REDACTED]

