- a decrease of the area of enhancing or non-enhancing lesion on T2 or FLAIR MR imaging between 25% and 50% compared with baseline
- no new lesions, no new T2 or FLAIR abnormalities apart from those consistent with radiation effect, and no new or increased enhancement; **and**
- subject should be on a corticosteroid dose that should not be greater than the dose at time of baseline scan, and should be stable or improved clinically

Stable disease (SD): Stable disease (SD) is present if the changes do not qualify for CR, PR, MR or progression and requires:

- stable area of enhancing or non-enhancing abnormalities on T2 or FLAIR imaging
- no new lesions, no new T2 or FLAIR abnormalities apart from those consistent with radiation effect, and no new or increased enhancement
- subject should be on a corticosteroid dose that should not be greater than the dose at time of baseline scan, and should be stable or improved clinically

Disease progression (PD): Disease progression (PD) is defined by any of the following:

- development of new lesions or increase of enhancement (radiological evidence of malignant transformation)
- a 25% increase in the sum of the products of perpendicular diameters of the T2 or FLAIR enhancing or non-enhancing lesion on stable or increasing doses of corticosteroids compared with baseline scan or best response after initiation of therapy, not attributable to radiation effect or to comorbid events
- definite clinical deterioration not attributable to other causes apart from the tumour, or decrease in corticosteroid dose;
- or failure to return for evaluation because of death or deteriorating condition, unless caused by documented non-related disorders

References:

van den Bent MJ, Wefel JS, Schiff D, et al. Response assessment in neuro-oncology (a report of the RANO group): assessment of outcome in trials of diffuse low grade gliomas. *The Lancet*. 2011;12:583-593.

21.14 Appendix 14: RANO Response Criteria: Updated Response Assessment Criteria for WHO Grade 3 and 4 Glioma

Measureable disease is defined as bidimensionally contrast-enhancing or enhancing lesions with clearly defined margins by magnetic resonance imaging (MRI) scan, with two perpendicular diameters of at least 10 mm, visible on 2 or more axial slices that are preferably, at most, 5 mm apart with 0 mm skip.

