Non-measurable disease is defined as either unidimensionally measurable lesions, masses with margins not clearly defined, or lesions with maximal perpendicular diameters less than 10 mm.

All measurable and non-measurable lesions must be assessed using the same techniques as at baseline.

Complete response (CR): Requires all of the following:

- complete disappearance of all enhancing measurable and non-measurable disease sustained for at least 4 weeks
- no new lesions
- stable or improved non-enhancing (T2/FLAIR [fluid attenuated inversion recovery]) lesions
- subjects must be off corticosteroids (or on physiologic replacement doses only)
- stable or improved clinically.

Note: Subjects with non-measurable disease only cannot have a CR; the best response possible is stable disease (SD).

Partial response (PR): Requires all of the following:

- $\geq 50\%$ decrease compared with baseline, in the sum of products of perpendicular diameters of all measurable enhancing lesions sustained for at least 4 weeks
- no progression of non-measurable disease; no new lesions
- stable or improved non-enhancing (T2/FLAIR) lesions on same or lower dose of corticosteroids compared with baseline scan

- corticosteroid dose at the time of the scan evaluation should be no greater than the dose at time of baseline scan
- stable or improved clinically.

Note: Subjects with non-measurable disease only cannot have a PR; the best response possible is SD.

Stable disease (SD): Requires all of the following:

- does not qualify for CR, PR, or progression
- stable non-enhancing (T2/FLAIR) lesions on same or lower dose of corticosteroids compared with baseline scan.

In the event that the corticosteroid dose was increased for new symptoms and signs without confirmation of disease progression (PD) on neuro-imaging, and subsequent follow-up imaging shows that this increase in corticosteroids was required because of PD, the last scan considered to show SD will be the scan obtained when the corticosteroid dose was equivalent to the baseline dose.

NOTE: Stable doses of corticosteroids include subjects not on corticosteroids.

Disease progression (PD): Disease progression (PD) is defined by any of the following:

- $\geq 25\%$ increase in sum of the products of perpendicular diameters of enhancing lesions compared with the smallest tumor measurement obtained either at baseline (if no decrease) or best response, on stable or increasing doses of corticosteroids

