- significant increase in T2/FLAIR non-enhancing lesion on stable or increasing doses of corticosteroids compared with baseline scan or best response after initiation of therapy not caused by co-morbid events (e.g., radiation therapy, demyelination, ischemic injury, infection, seizures, post-operative changes, or other treatment effects)
- any new lesion; clear clinical deterioration not attributable to other causes apart from the tumor (e.g., seizures, medication adverse effects, complications of therapy, cerebrovascular events, infection) or changes in corticosteroid dose
- failure to return for evaluation as a result of death or deteriorating condition

- clear progression of non-measurable disease.

Summary of RANO Response Criteria

Criterion	CR	PR	SD	PD
T1 gadolinium-enhancing disease	None	≥50% decrease	<50% decrease but <25% increase	≥25% increase ¹
T2/FLAIR	Stable or decrease	Stable or decreasing	Stable or decrease	Increase
New Lesion	None	None	None	Present
Corticosteroids	None	Stable or decreasing dose	Stable or Decreasing dose	NA ²
Clinical Status	Stable or increase	Stable or increase	Stable or increase	Decrease
Requirement for Response	All	All	All	Any

Abbreviations: CR = complete response; FLAIR = fluid-attenuated inversion recovery; NA = not applicable; PD = progressive disease; PR = partial response; RANO = Response Assessment in Neuro-Oncology; SD = stable disease

Progression occurs when this criterion is present.

Increase in corticosteroids alone will not be taken into account in determining progression in the absence of persistent clinical deterioration.

References:

Wen PY. Updated Response Assessment Criteria for High-Grade Gliomas: Response Assessment in Neuro-Oncology Working Group. *J Clin Oncol.* 2010;28(11):1963-1972.

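### In both glioma cohorts the SAP censors clinical-only progression that the protocol's RANO criteria count as PD, does not declare the change, and so tends to overstate PFS and DoR

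*SAP*

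**What the plan says.** Protocol 18.3.3.2: "Progression-free survival (PFS) is defined as the time from the date of enrollment to the earliest date of progression or death". Nothing there limits progression to imaging. The same section adds: "Further details on rules for censoring will be provided in the RAP".

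Protocol Appendix 13 (WHO Grade 1 or 2 glioma) and Appendix 14 (Grade 3 and 4) share one construction: "Disease progression (PD) is defined by any of the following". One item in the Appendix 13 list is "definite clinical deterioration not attributable to other causes apart from the tumour". One item in Appendix 14 is "clear clinical deterioration not attributable to other causes apart from the tumor". The summary table in Appendix 14 repeats this: worsened clinical status is in the PD column, and any single entry is enough.

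SAP 2.6.1: "For the cohorts assessed using RECIST 1.1 and RANO criteria, the analysis of DoR will be based on radiological response from investigator assessment". SAP 2.6.2 dates progression from imaging and says: "Clinical progression, defined as investigator assessed clinical progression in the absence of radiological confirmation, is not considered a progression event in this analysis". Both sections censor such subjects at the last scan if the scans do not show progression. The sentence just before the exclusion in 2.6.2 reads: "Subjects who do not meet the RECIST 1.1 or RANO criteria for progression and are still alive will be censored".

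SAP Section 3 reports that the protocol's analyses are unchanged.

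**The concern.** A glioma subject with tumour-related clinical decline has PD under the protocol and is progression-free under the SAP. The SAP applies one rule to two response systems that treat clinical decline differently. RECIST in Appendix 10 keeps symptomatic deterioration apart from objective response status, so the rule is right for those cohorts. RANO does not make that separation.

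The asymmetry also matters for DoR. CR and PR in both glioma appendices require a stable or improved clinical state. Clinical status therefore helps decide whether a response is granted, but its loss cannot end the response.

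Subjects censored this way are at high risk of progression or death soon afterwards. Removing them at the preceding scan breaks the independence that Kaplan-Meier censoring assumes, and the bias tends to favour the treatment. Amendment 11 extended the study to obtain more mature DoR, PFS and OS. Protocol 18.4.2.2 leans on the secondary efficacy endpoints where statistical success comes with only a moderate response rate.

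**Working it through.** **1. Is it a change of event or a censoring detail?** The protocol leaves censoring rules to the RAP. Appendices 13 and 14 define what PD is. The SAP rule removes one of the listed PD criteria, so it alters the event. Within 2.6.2, one sentence censors those who do not meet RANO progression, and the next excludes a case that does meet it.

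**2. Would the planned outputs reveal it?** The sensitivity analysis is an independent radiology review derived in a similar way, so it cannot restore clinical PD. The four censoring reasons named in 2.6.1 and 2.6.2 have no clinical-only entry. Such cases would fall under new therapy before documented PD, or under no progression or death.

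**3. Direction.** Let n subjects be at risk at the last scan, with k other events before the clinical PD date. By that date the Kaplan-Meier curve is multiplied by:
- clinical PD as an event: (n − k − 1)/n
- censored at the earlier scan: (n − k − 1)/(n − 1)

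For n = 10 and k = 3 this gives 6/10 = 0.600 against 6/9 = 0.667. From the clinical PD date onwards the second factor is never the smaller. Between the scan and that date the curve can be marginally lower.

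**4. Size.** The plan gives no figure to reproduce.

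Inputs from the documents:
- scans every 8 weeks to week 48, then every 12 weeks, and at the Follow-up Visit (Protocol 7.1, note 27)
- missed-assessment windows of 119, 147 and 175 days (SAP Table 4-1)
- 30.4375 days per month (SAP 2.1.1)

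Assumptions:
- exponential time to progression, true median 9 months
- clinical-only share f of 5% to 30%
- median survival after deterioration 3 months
- a later death counts only if no new therapy has started and it falls within the window

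Two rows have a closed form. With λ = ln 2/9, one 8-week interval has q = exp(−λ × 56/30.4375) = 0.8679. Month 12 lies between the week 48 and week 60 scans.
- Protocol RANO: f·exp(−12λ) + (1 − f)·q⁶. At f = 0.20: 0.2 × 0.3969 + 0.8 × 0.4273 = 0.421.
- Upper bound (no later scan shows PD, everyone starts new therapy): [q/(1 − f(1 − q))]⁶. At f = 0.20: (0.8679/0.9736)⁶ = 0.8914⁶ = 0.502.

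Rows (a) to (c) come from simulation. Each later scan shows PD with probability 0.5.

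| 12-month PFS, by clinical-only share | 5% | 10% | 20% | 30% |
|---|---|---|---|---|
| Protocol RANO | 0.426 | 0.424 | 0.421 | 0.418 |
| (a) Follow-up Visit scan, then 12-weekly scans | 0.430 | 0.431 | 0.434 | 0.439 |
| (b) Follow-up Visit scan only | 0.431 | 0.435 | 0.442 | 0.449 |
| (c) as (a), but half start new therapy after the Follow-up Visit scan | 0.433 | 0.440 | 0.453 | 0.466 |
| Upper bound | 0.445 | 0.463 | 0.502 | 0.545 |

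If the Follow-up Visit scan shows PD in everyone scanned, the SAP figure is 0.426 to 0.427, an excess of 0.001 to 0.008 across the shares. Median survival of 6 rather than 3 months after deterioration moves (c) at 20% only from 0.453 to 0.454.

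Other settings at a 20% share:

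| Setting | RANO | (a) | (c) | Upper |
|---|---|---|---|---|
| PFS, median 4 months, at 12 months | 0.143 | 0.155 | 0.168 | 0.207 |
| PFS, median 18 months, at 24 months | 0.421 | 0.429 | 0.448 | 0.503 |
| DoR, median 12 months, at 12 months | 0.501 | 0.513 | 0.529 | 0.571 |

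The SAP rule gave the higher estimate in every setting.

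**5. Which row applies?** This is unsettled. Protocol 16.3 and note 58(b) of the Time and Event Table continue 12-weekly assessments only when treatment stops before or without progression. If clinical deterioration is PD, as the appendices say, Section 16.3 lists no further scans and (b) is nearer. If sites do not treat it as PD, (a) or (c) is nearer.

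**The case against.** The rule is stated openly, and imaging-dated progression is a reasonable guard against subjective calls in an open-label trial. Section 18.3.3.2 does not cite the glioma appendices when it defines PFS, and it leaves both censoring and possible sensitivity analyses to the RAP. One can therefore read the SAP as supplying the deferred detail. In context, the RANO wording in 2.6.2 may simply mean RANO's imaging criteria. Subject listings, swim-lane plots and tables of reasons for stopping treatment would let a patient reader find some of these cases, and the table shells, which are not among the documents, may add a row. The number affected could be zero. The plausible excess is also small beside sampling error: the standard error of a 0.42 estimate is about √(0.42 × 0.58/25) = 0.10 with 25 subjects, and 0.07 with 50 (assumed sizes).

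Much of this stands as a limit on severity. It does not remove the point. Deferring censoring rules does not cover dropping a listed PD criterion, and sampling error does not excuse a bias with a known direction. Listings do not give an estimate under the protocol's own definition. The Follow-up Visit scan is already credited in (a) to (c), and an excess remains.

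**Conclusion.** The concern holds, for the two glioma cohorts only. SAP 2.6.1 and 2.6.2 narrow the protocol's RANO progression event, Section 3 does not say so, and the effect tends to overstate PFS and DoR.

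The size in this trial cannot be derived from the documents. With a true median of 9 months, the excess in 12-month PFS runs from about 0.001 to 0.02 at a 5% share and from about 0.005 to 0.08 at 20%. The upper ends need every affected subject to start new therapy with no scan showing PD, which is unlikely. These figures rest on the assumed share, the scan-detection probability, the use of new therapy, and later deaths counting as events. The SAP does not say whether a death overrides the clinical-progression censoring.

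PFS and DoR are secondary and descriptive, and neither the ORR decision rule nor OS is touched. This should be fixed, but it does not undermine the trial's main conclusion.

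**What to change.** Keep radiological progression as the main analysis if preferred, and:

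1. List it in SAP Section 3 as a departure from the PD definitions in Appendices 13 and 14.
2. For both glioma cohorts, prespecify a sensitivity analysis of investigator-assessed PFS and DoR with full protocol-RANO PD as the event, dating clinical deterioration at the assessment that recorded it.
3. Add a clinical-only progression row, with counts, to the censoring-reason tables in 2.6.1 and 2.6.2.
4. Reconcile the two adjacent sentences in 2.6.2.

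Leave the RECIST and MM cohorts as they are.

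The cost is SAP wording, one derivation and one table row. SAP 2.6.2 implies that clinical progression is recorded; check that the eCRF, which is not among the documents, holds it with a date. The added glioma estimates may be slightly less favourable.
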